Alcohol breath, urine drug screening and urine cotinine testing	X	X						
 • Alcohol breath test will be performed at the discretion of the investigator. • Urine cotinine (mandatory) will be performed at Screening, and on Period 1 Day -1. This test may be performed at any other time at the discretion of the investigator.

PFIZER CONFIDENTIAL

CT02-GSOP Clinical Pharmacology Protocol Template (14 April 2023)

Table 1. Study Schedule of Assessment

Visit Identifier Abbreviations used in this table may be found in Appendix 12 .	Screen	Period 1		Period 2		Telephone F/U	Early Discontinuation	Notes
Days Relative to Day 1	Day - 28 to Day -2	Day - 1	Day 1	Day 2	Day 3	Day 30-37		
 • All screening should be done \leq28 days before the first dose. • Day relative to start of study intervention (Day 1). • Follow-up may occur via telephone contact and must occur 28-35 days after administration of the final dose of study intervention.
Days within each period		Day - 1	Day 1	Day 1	Day 2			
HIV, HBsAg, HBsAb, HBcAb, HCVAb	X							
 • HBsAb is to be run if HBsAg and/or HBcAb are positive.
Retained Research Sample for Genetics (Prep D1)			X					
Study intervention administration			X	X				
PK blood sampling			X	X			X	
 • See Table 2 for details. • Period 2 Day 1 PK sample will be 24 hr post dosing in Period 1 Day 1. Sample will be collected for Japanese participants only.
CRU discharge					X			
 • Discharge from CRU after completing protocol-required activities on the day.
Serious and nonserious AE monitoring	X	→	→	→	X	X	X	
 • See Section 8.4.3 for follow-up AE and SAE assessments.

Table 2. Pharmacokinetic Sampling Timepoints

Visit Identifier												Notes
Study Day	Day 1										Day 2	
Days within each period	Period 1, Day 1										Period 2, Day 1	
Time Before/After Dose	0 h	0.25 h	0.5 h	1 h	1.5 h	2 h	3 h	4 h	6 h	8 h	12 h	24 h
Study intervention administration	X											
Venous PK sampling	X ^b	X ^b	X	X	X ^b	X	X ^b	X	X ^b	X	X	X ^b
Tasso PK sampling ^a			X	X		X		X		X	X	
Blood: plasma ratio				X					X			

a. Tasso PK sampling will be performed using either Tasso-Plus or Tasso-M20 device.

b. To be collected for Japanese participants only.

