2.2.2.3. Clinical Pharmacology

Based on the completed clinical studies of IN and PO zavegeptan, the following observations were made regarding the zavegeptan PK properties. Zavegeptan is rapidly absorbed (T_{max} : 0.54 hours) following a single zavegeptan 10 mg IN dose. The terminal elimination half-life of zavegeptan 10 mg IN dose is approximately 3 hours.³⁵ While the effective half-life of zavegeptan, which is considered more clinically relevant than the elimination half-life as it takes into account the entire plasma concentration-time profile, ranged from approximately 5 to 8 hours across dose levels ranging from 5 to 40 mg IN. Zavegeptan exhibits less than dose-proportional increases in exposure following single IN dose administration over the dose range from 1 mg to 40 mg. No evidence of meaningful accumulation was observed across a dose range of 5 to 20 mg zavegeptan IN after repeated QD dosing.

The results of the DDI study showed that co-administration of sumatriptan with zavegeptan IN does not result in a meaningful change in the PK of sumatriptan or of zavegeptan.

Co-administration of sumatriptan with zavegeptan IN does not cause elevations in mean arterial blood pressure or of systolic or diastolic blood pressure greater than those observed with sumatriptan alone. Lack of a clinically significant effect on the exposures of EE and LNG following co-administration of zavegeptan 20 mg IN and oral contraceptive support that zavegeptan is not a clinically relevant inhibitor of CYP3A4. Zavegeptan may be administered with an oral contraceptive without dose frequency adjustment. A 16% increase in the C_{max} and a 1.9-fold increase in zavegeptan AUC were observed in participants with moderate hepatic impairment.

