8.5. Pharmacokinetics

Venous blood samples of approximately 4 mL, to provide approximately 1.5 mL plasma, will be collected for measurement of plasma concentrations of zavege pant as specified in the

SoA. Prior to centrifugation of blood samples collected at the time points specified in the **SoA, Table 2**, a 500 µL portion of the PK blood sample will be aliquoted and used to determine the blood-to-plasma ratio of zavegeptan. Determining the blood-to-plasma ratio will be crucial for converting the dried blood concentrations collected using Tasso-M20 to their equivalent plasma concentrations for adequate comparison between the 2 methods. For Tasso sampling, approximately 100 µL of blood will be collected from participants using the Tasso-M20 devices, while for Tasso-Plus, approximately 300-500 µL of blood will be collected to provide approximately 150 - 200 µL serum into appropriately labeled tubes for the measurement of zavegeptan concentration as specified in the **SoA, Table 2**. Of note, both Tasso and venous PK samples will be collected at the same time. Instructions for the collection and handling of biological samples will be provided in the laboratory manual or by the sponsor. The actual date and time (24-hour clock time) of each sample will be recorded.

All efforts will be made to obtain the samples at the exact nominal time relative to dosing. Collection of samples up to and including 10 hours after dose administration that are obtained within 10% of the nominal time relative to dosing (eg, within 6 minutes of a 60-minute sample) will not be captured as a protocol deviation, as long as the exact time of the collection is noted on the source document and the CRF. Collection of samples more than 10 hours after dose administration that are obtained \leq 1 hour away from the nominal time relative to dosing will not be captured as a protocol deviation, as long as the exact time of the collection is noted on the source document and the CRF. This protocol deviation window does not apply to samples to be collected more than 10 hours after dose administration at outpatient/follow-up visits with visit windows.

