2.3. Study Design

This is a single-center, Phase 1, non-randomized, open-label, 2-period study in healthy participants to primarily evaluate the correlation of zavegepant concentration from samples collected using Tasso Devices (Tasso-Plus and Tasso-M20) compared to standard venous phlebotomy. This study consists of two periods which will include approximately 14 participants.

In period 1, 50% (n=7) of participants will use Tasso-Plus, while the other 50% (n=7) will use Tasso-M20. All 14 participants will have 6 PK samples collected using the assigned Tasso device simultaneously with collecting venous blood samples at the following time points, 30 minutes, 1, 2-, 4-, 8-, and 12-hour postdose, as described in the SoA, Table 2 (in the protocol). In addition, taste assessments will be performed at time intervals of 1 (immediately after dosing), 5, 10 and 20 minutes after zavegepant IN administration. Also, if feasible, 4 Japanese participants will be enrolled among those 14 participants to evaluate the PK and safety of zavegepant IN in Japanese vs. non-Japanese participants. For Japanese participants, a total of 12 venous blood samples will be collected at the following time points, 0, 15 minutes, 30 minutes, 1, 1.5-, 2-, 3-, 4-, 6-, 8-, 12-, and 24-hour (refer to SoA, Table 2 in the protocol).

In period 2, a butterscotch candy will be given 5 minutes before administering the zavegepant IN study intervention. Taste assessment will also be performed after zavegepant IN administration with a butterscotch candy in period 2. For taste assessment, each participant will record the sensory attributes at timed intervals of 1 (immediately after dosing), 5, 10 and 20 minutes after zavegepant administration in each period.

Healthy participants will be screened within 28 days prior to the first administration of the study intervention to confirm that they meet the participant selection criteria for the study. Eligible participants will be admitted to the CRU on Day -1 and will be confined in the CRU until Discharge on Day 3 (SoA in the protocol), approximately 24 hours after the second dose. Enrolled participants will receive a single IN dose of zavegepant 10 mg (0.1 mL) in each period. PK venous blood samples as well as Tasso PK sampling, using Tasso-Plus and

Tasso-M20, will be collected at specified intervals as per SoA (Table 2) in the protocol for PK assessments.

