3.1.2. Zavegepant PK Parameters

Zavegepant PK parameters from samples collected using Tasso and venous phlebotomy will be derived from the concentration-time profile using non-compartmental methods, as detailed in Table 2. Actual PK sampling times will be used in the derivation of PK parameters. In the case that actual PK sampling times are not available, nominal PK sampling time will be used in the derivation of PK parameters.

Table 2. Definitions of PK Parameters

Parameter	Definition	Method of Determination
C_{max}	Maximum plasma concentration	Observed directly from data
AUC_{last}	Area under the plasma concentration-time profile from time 0 to the time of the last quantifiable concentration (C_{last})	Linear/Log trapezoidal method
AUC_{inf}^a	Area under the plasma concentration-time profile from time 0 extrapolated to infinite time	$AUC_{last} + (C_{last}/k_{el})$, where C_{last} is the predicted plasma concentration at the last quantifiable time point estimated from the log-linear regression analysis
T_{max}	Time for C_{max}	Observed directly from data as time of first occurrence
$t_{1/2}^a$	Terminal half-life	$\log_2(2)/k_{el}$, where k_{el} is the terminal phase rate constant calculated by a linear regression of the log-linear concentration-time curve
CL/F^a	Apparent clearance	Dose/ AUC_{inf}
V_z/F^a	Apparent volume of distribution	Dose/($AUC_{inf} \times k_{el}$)

a. If data permits.

PK parameters from samples collected using Tasso-M20 will be adjusted for B/P ratio.

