6.1.2. Zavegepant PK Parameters

The PK parameters of zavegepant will be listed and summarized descriptively for each collection method (Tasso-Plus, Tasso-M20 and venous phlebotomy), and by race (non-Japanese and Japanese), as data permits for the PK Parameter Analysis Set. Each zavegepant PK parameter will be summarized including the set of summary statistics as specified in Table 3.

For AUC_{last} , AUC_{inf} , and C_{max} , box and whisker plots for individual participant parameters will be constructed for each collection method and overlaid with geometric means.

Table 3. PK Parameters to be Summarized Descriptively by Collection Method and Race

Parameter	Summary Statistics
AUC_{inf} , AUC_{last} , C_{max} , CL/F , V_z/F	N, arithmetic mean, median, SD, %CV, minimum, maximum, geometric mean and geometric %CV
T_{max} , T_{last}	N, median, minimum, maximum
$t_{1/2}$	N, arithmetic mean, median, SD, %CV, minimum, maximum

Supporting data from the estimation of $t_{1/2}$ and AUC_{inf} will be listed by collection method and by race: terminal phase rate constant (k_{el}); goodness of fit statistic from the log-linear regression (r^2); the percent of AUC_{inf} based on extrapolation ($AUC_{extrap}\%$); and the first, last, and number of time points used in the estimation of k_{el} . This data may be included in the clinical study report.

For the Tasso vs. Venous comparison, natural log-transformed zavegepant AUC_{inf} (if data permit), AUC_{last} and C_{max} will be analyzed using a mixed effect model with blood collection method as fixed effect and participant as random effect. Estimates of the adjusted mean differences (Test – Reference) and corresponding 90% CIs will be obtained from the model with Venous as the Reference group and Tasso-M20 (or Tasso-Plus) as the Test group. The adjusted mean differences and 90% CIs for the differences will be exponentiated to estimate the adjusted geometric means ratio (Test/Reference) and 90% CIs for the ratios.

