For race comparison, natural log-transformed zavegepant AUC_{inf} (if data permit), AUC_{last} and C_{max} will be analyzed using an ANOVA model with race as fixed effect. Estimates of the adjusted mean differences (Test – Reference) and corresponding 90% CIs will be obtained from the model with non-Japanese as the Reference group and Japanese as the Test group. The adjusted mean differences and 90% CIs for the differences will be exponentiated to estimate the adjusted geometric means ratio (Test/Reference) and 90% CIs for the ratios.

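### The race and Tasso-venous AUClast ratios in SAP 6.1.2 can compare 0-24 h with 0-12 h profiles, because no common AUC window is set

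*SAP*

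**What the plan says.** **Race model.** SAP 6.1.2 estimates a Japanese/non-Japanese geometric mean ratio with a 90% CI for AUCinf (if data permit), AUClast and Cmax. The log parameters "will be analyzed using an ANOVA model with race as fixed effect". No other term is listed, and the matrix (venous, Tasso-Plus or Tasso-M20) is not named.

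**Tasso-venous model.** The same section uses a "mixed effect model with blood collection method as fixed effect and participant as random effect" for the same three parameters, with venous as reference.

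**Sampling.** All participants have paired Tasso and venous draws at 0.5, 1, 2, 4, 8 and 12 h. SAP 2.3 adds: "For Japanese participants, a total of 12 venous blood samples will be collected at the following time points", and lists 0, 0.25, 0.5, 1, 1.5, 2, 3, 4, 6, 8, 12 and 24 h. In Protocol 1.3, Table 2, the extra venous draws (0, 0.25, 1.5, 3, 6 and 24 h) carry the footnote "To be collected for Japanese participants only". Tasso draws stop at 12 h for every participant.

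**Parameter.** SAP 3.1.2 defines AUClast as "Area under the plasma concentration-time profile from time 0 to the time of the last quantifiable concentration". It also says: "Actual PK sampling times will be used in the derivation of PK parameters". Neither document defines AUC0-12 or any other common window.

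**The concern.** AUClast depends on how long a profile is followed. Under this schedule the follow-up of a venous profile is fixed by race, so race and sampling window are fully confounded. No term added to the model could separate them. Only a common-window derivation can.

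Protocol 4.2 says that no PK data exist for the intranasal product in Japanese participants and that these data will support development in Japan. An AUClast ratio above 1 could then be read as higher Japanese exposure when part or all of it comes from the extra 12 hours. The 90% CI conveys imprecision but not this shift.

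The same omission reaches the Tasso-venous model. A Japanese participant's venous AUClast can run to 24 h while the paired Tasso AUClast ends at 12 h. That pushes the device ratio below 1 in a comparison that serves the primary objective.

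**Working it through.** **The plan's own figure.** Protocol 4.2 says that 24 h covers more than 3 half-lives in Japanese participants. 24/6.55 = 3.66 and 24/3 = 8.0, so the statement reproduces on either half-life.

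**Inputs.** Tmax is 0.54 h (Protocol 2.2.2.3 and 4.2). The same section 2.2.2.3 states that the terminal half-life for the "10 mg IN dose is approximately 3 hours" and gives effective half-lives of about 5-8 h. Protocol 4.2 gives 6.55 h for the effective half-life at 10 mg. AUC is by linear/log trapezoids (SAP Table 2). No LLQ is given. Assumed here: C(0) = 0, linear-up/log-down integration, and identical true PK in both groups.

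**Step 1: tail only, single exponential.** AUC0-24/AUC0-12 = (1 - 2^(-24/t)) / (1 - 2^(-12/t)).
- t = 3 h: 0.9961/0.9375 = 1.06
- t = 5 h: 1.19
- t = 6.55 h: 1.28
- t = 8 h: 1.35

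**Step 2: actual venous schedules.** One-compartment profile with Tmax 0.54 h and Cmax scaled to 1.

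| Half-life | Japanese, to 24 h | Japanese, to 12 h | Non-Japanese, to 12 h | AUClast ratio | Ratio if 24 h BLQ | C24/Cmax |
|---|---|---|---|---|---|---|
| 3 h | 4.842 | 4.544 | 4.451 | 1.088 | 1.021 | 0.46% |
| 5 h | 7.447 | 6.231 | 6.132 | 1.214 | 1.016 | 3.9% |
| 6.55 h | 9.161 | 7.114 | 7.013 | 1.306 | 1.014 | 8.5% |
| 8 h | 10.522 | 7.729 | 7.626 | 1.380 | 1.013 | 13.2% |

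The small remainder in the BLQ column comes from the denser Japanese draws before 12 h.

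**Step 3: two-phase profiles held at Tmax 0.54 h.** These have an assumed faster early phase.
- Late half-life 3 h: AUClast ratio 1.04-1.08, or 1.02-1.03 if 24 h is BLQ. C24 is only 0.06-0.34% of Cmax.
- Late half-lives of 5-8 h: 1.08-1.34, or 1.01-1.02 if BLQ.

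**Step 4: the other parameters.**
- Cmax: ratio 1.00 without noise, since both schedules sample at 0.5 h, and 1.02-1.06 under assumed noise.
- AUCinf: 0.94-1.12 across scenarios, with no fixed direction.

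**Step 5: Tasso-venous model.** Assume each device is analysed as pairs, with m of 7 participants Japanese, and let R be the ratio from step 2. With identical concentrations the Tasso/venous AUClast ratio is R^(-m/7).
- m = 2: 1.088^(-2/7) = 0.98 (3 h); 1.306^(-2/7) = 0.93 (6.55 h)
- m = 4: 1.088^(-4/7) = 0.95; 1.306^(-4/7) = 0.86

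The documents do not say how Japanese participants are split between devices.

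**Step 6: precision of the race ratio.** With 4 versus 10 participants (12 df), the 90% CI factor is exp(1.782 × sqrt(ln(1 + CV²)) × sqrt(1/4 + 1/10)). This gives 1.36 at CV 30%, 1.65 at 50% and 1.95 at 70%. The CVs are assumed.

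**Step 7: common window.** With the six shared times in both groups, the schedule-only ratio is 1.00 by construction. Cutting at 12 h but keeping the extra Japanese draws leaves 1.01-1.02 (one-compartment). In two-phase profiles where Tmax was not held at 0.54 h, it leaves 1.00-1.09.

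**The case against.** **The matrix is not stated.** If the race model used Tasso parameters, both groups would share the same six times and the race shift would not arise. This stands as a condition. Venous is still the natural reading: the race model has no participant term, which implies one record per participant, and the 24 h Japanese profile exists only in venous plasma.

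**The 24 h sample may be unquantifiable.** At the stated terminal half-life it is below 0.5% of Cmax, and no LLQ is given. If it is BLQ, little is left. This also stands, although Protocol 4.2 relies on the 24 h draw to estimate half-life in Japanese participants.

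**The large ratios borrow the wrong half-life.** A reader might infer an inflation of 20-40%. The documents do not support that as the expected size: Protocol 2.2.2.3 separates the terminal half-life from the effective one, and the larger ratios need the late decline to follow the latter.

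**Other outputs help.** AUCinf is not tied to the last sample, but it is conditional on the data. Tlast and AUCextrap% by race reveal unequal follow-up without correcting AUClast.

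**Stakes are limited.** Japanese enrolment is optional, race is absent from the objectives table, no hypothesis is tested, and at about 3 h the shift lies well inside the CI factor of 1.36-1.95. This lowers the urgency. It does not justify a ratio whose direction is partly set by the schedule.

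**Conclusion.** The concern holds, with conditions, and should be fixed. If venous parameters are used and 24 h is quantifiable, the race AUClast ratio is shifted upward by the schedule alone. The shift is about 1.04-1.09 at the stated 3 h terminal half-life, and up to about 1.2-1.4 (one-compartment) only if the late decline followed the 5-8 h effective half-life. If 24 h is BLQ it is about 1.01-1.03. These are scenarios under assumed profiles, not bounds.

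The Tasso-venous AUClast ratio carries the same shift inverted: about 0.98 or 0.93 with 2 of 7 Japanese participants on a device, and 0.95 or 0.86 with 4 of 7 (3 h or 6.55 h).

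Two further inferences would go too far. A reader might conclude that the whole primary comparison is compromised. The concentration correlations and Bland-Altman analysis use paired samples at the six shared times, so they are not exposed, and with no Japanese participants enrolled the problem disappears. A reader might also extend the claim to Cmax and AUCinf. Cmax is unaffected without noise, and AUCinf has no fixed direction of bias.

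**What to change.** In SAP 6.1.2:

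1. State that the race model uses venous plasma parameters, one record per participant.
2. Base the AUC ratio in both the race model and the Tasso-venous model on AUC0-12, derived in every profile from 0.5, 1, 2, 4, 8 and 12 h. Set the time-zero concentration to 0 throughout, since non-Japanese venous profiles and all Tasso profiles have no predose draw.
3. Give one rule for reaching 12 h, consistent with the BLQ convention in SAP 5.3.1. It is needed because actual times are used and, under Protocol 8.5, a 12 h draw up to "1 hour away from the nominal time relative to dosing will not be captured as a protocol deviation". In the one-compartment case, a draw at 11 h or 13 h changes that participant's area by -1.9%/+1.5% (3 h) or -4.5%/+4.1% (6.55 h).
4. Report Cmax from the six shared times beside Cmax from all draws.
5. Keep full-schedule AUClast and AUCinf as supportive, with Tlast and AUCextrap% beside the race ratio, and keep the 24 h data for half-life.

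The cost is SAP wording and one extra derivation from data already planned, with no added samples or participants. The downside is that the Japanese-only draws do not enter the AUC0-12 comparison.

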6.2. Secondary Endpoints

6.2.1. Safety Endpoints

Safety data will be analyzed on Safety Analysis Set in accordance with the CaPS (see [Section 6.5](#)).

6.2.2. Other Endpoint

The sensory attributes (overall liking, bitterness, tongue/mouth burn, throat burn, sour taste, salty taste, and sweet taste) from the Taste Assessment Questionnaire will be listed and descriptively summarized by study intervention (zavegepan alone vs zavegepan + butterscotch candy) and time points.

Summary statistics (mean and 90% CI) will be calculated for the various questions. Radar plots for each of 4 time points (1, 5, 10 and 20 minutes after dosing), summarizing all attributes for each intervention will be generated. Boxplots of each attribute will be plotted against the time points.

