Previous case studies have shown that simple interventions like sucking butterscotch or drinking a fruit punch–flavored powdered drink have successfully managed dysgeusia following the use of sumatriptan or esketamine nasal sprays, respectively.^{37,38} Therefore, finding strategies to mask zavegeptan-induced bitter taste can help improve patient experience and adherence. As an exploratory objective, this study will explore whether giving a butterscotch candy before zavegeptan IN administration will help manage dysgeusia. To do that, a second dose of 10 mg zavegeptan IN will be administered 24 hours after the first dose. Participants will be instructed to eat a butterscotch candy approximately 5 minutes prior to zavegeptan IN administration in period 2. Taste assessments will be compared for the 14 subjects after zavegeptan administration alone in period 1 vs. zavegeptan and butterscotch candy in period 2. Administering a second dose of 10 mg zavegeptan IN 24 hours after the first dose is well-supported by zavegeptan IN clinical trials data which shows no dose-limiting AEs after administering single doses as high as 40 mg IN and multiple doses of 20 mg for up to 14 days (refer to IB).

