6.1. Study Intervention(s) Administered

Zavegeptan is formulated as 10 mg for IN single-dose administration. The study intervention will be provided in single-use unidose nasal spray devices fully prepared and ready for administration.

Study Intervention(s)	
Intervention Name	Zavegeptan
Type	Drug
Use	Experimental
IMP or NIMP/AxMP	IMP
Dose Formulation	Nasal spray
Unit Dose Strength(s)	10 mg
Dosage Level(s)	10 mg
Route of Administration	IN

Study Intervention(s)	
Sourcing	Provided centrally by the sponsor. Refer to the IP manual.
Packaging and Labeling	Study intervention will be provided in unidose nasal spray. Each nasal spray will be labeled according to local regulatory requirements. Study intervention will be provided to the site as bulk labeled nasal spray for dispensing by the pharmacy and administration by site personnel.
SRSD	USPI
Current Name or Alias	Zavege pant

Study Arm(s)	
Arm Title	Zavege pant
Arm Description	All participants will receive zavege pant 10 mg IN spray in period 1 and a butterscotch candy + zavege pant 10 mg IN spray in period 2

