2.2. Study Objectives, Endpoints, and Estimands

The following are the objectives and endpoints in this study. Estimand framework will not be applied to this Phase 1 study in healthy participants.

Objectives	Endpoints
Primary:	Primary:

 Characterize the PK profile of zavegepant from samples collected using Tasso Devices (Tasso-Plus and Tasso-M20) vs. standard venous phlebotomy following IN administration of 10 mg of zavegepant IN formulation in healthy participants 	
 Zavegepant concentrations from samples collected using Tasso devices vs. standard venous phlebotomy AUC_{last}, C_{max}, T_{max}, $t_{1/2}$, CL/F and V_z/F, as data permits

Objectives	Endpoints
Secondary:	Secondary:

 Evaluate the safety and tolerability following IN administration of 10 mg of zavegepant IN formulation in healthy participants 	
 Assessment of TEAEs, and clinical safety laboratory tests
Exploratory:	Exploratory:

 Evaluate the effect of the administration of 10 mg of zavegepant IN with a butterscotch candy on dysgeusia compared to zavegepant IN alone 	
 Taste Assessment Survey Scoring Metrics after study intervention: overall liking, bitterness, tongue/mouth burn, throat burn, sour taste, salty taste, and sweet taste

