4. ANALYSIS SETS (POPULATIONS FOR ANALYSIS)

Data for all participants will be assessed to determine if participants meet the criteria for inclusion in each analysis population prior to releasing the database and classifications will be documented per standard operating procedures.

Participant Analysis Set	Description
Enrolled	“Enrolled” means a participant’s, or their legally authorized representative’s, agreement to participate in a clinical study following completion of the informed consent process and assignment to study intervention. A participant will be considered enrolled if the informed consent is not withdrawn prior to participating in any study activity. Potential participants who are screened for the purpose of determining eligibility for the study, but do not participate in the study, are not considered enrolled, unless otherwise specified by the protocol.
PK Concentration Analysis Set	All enrolled participants who receive 1 single IN dose of zavegepan and provide at least 1 evaluable plasma concentration.
PK Parameter Analysis Set	All enrolled participants who receive 1 single IN dose of zavegepan and provide at least 1 evaluable PK parameters of interest.
Taste Assessment Set	All participants who receive at least 1 single IN dose of zavegepan and complete the Taste Assessment Questionnaire
Safety Analysis Set	All participants who take at least 1 dose of study intervention. Participants will be analyzed according to the product they actually receive.

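### SAP 6.2.2 summarises taste scores separately with and without candy and plans no within-participant difference with a 90% CI, although the exploratory objective is that comparison in the same participants

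*SAP*

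**What the plan says.** The exploratory objective in SAP 2.2 (and Protocol 3) is a contrast: "Evaluate the effect of the administration of 10 mg of zavegepant IN with a butterscotch candy on dysgeusia compared to zavegepant IN alone". Protocol 4.2 makes it a comparison in the same people: "Taste assessments will be compared for the 14 subjects after zavegeptan administration alone in period 1 vs. zavegeptan and butterscotch candy in period 2". The arm description in Protocol 6.1 gives everyone the "IN spray in period 1 and a butterscotch candy" with a second spray in period 2, so the order is the same for all.

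For the analysis, SAP 6.2.2 plans listings and descriptive summaries of seven attributes by intervention and time point, radar plots and boxplots. On statistics it says only: "Summary statistics (mean and 90% CI) will be calculated for the various questions". Protocol 9.3.1 says the same, and SAP Appendix 1 enters taste data as descriptive statistics on observed data.

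The Taste Assessment Set (SAP 4) is defined as: "All participants who receive at least 1 single IN dose of zavegepan and complete the Taste Assessment Questionnaire". It does not say whether one period's questionnaire is enough or both are needed.

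For PK, SAP 6.1.2 does plan differences with 90% CIs. Tasso versus venous uses a "mixed effect model with blood collection method as fixed effect and participant as random effect". The race comparison uses an ANOVA.

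**The concern.** The objective asks about a difference, and the planned output is two separate columns of means. Each participant is their own control, but the plan does not use the pairing. A reader can subtract the two means, but cannot tell how precisely the difference is estimated.

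If anyone lacks period 2 data, the analysis set as worded could let that person contribute to one mean only. The subtraction would then no longer be a purely within-participant contrast.

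At stake is whether the study reports an interpretable interval for the candy contrast, which is the reason Protocol 4.2 gives for the second dose.

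**Working it through.** **The plan's own figures.** Protocol 9.5 gives 7 + 7 = 14 participants and 7 × 6 = 42 paired PK points per device. Both reproduce, but they concern PK. No SD, correlation, precision target or power is stated for taste.

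**Inputs**

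- From the documents: n = 14 (taken here as complete pairs), 90% confidence level (SAP 6.2.2), 0–100 scale (SAP 3.3), both conditions in every participant (Protocol 6.1).
- Assumed: a common SD *s* in both periods, 25 points for illustration (15 and 30 as a range), and within-participant correlation *r* from 0 to 0.7.
- Quantiles: t(0.95, 13) = 1.7709 and t(0.95, 26) = 1.7056.

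**Step 1: what is planned.** Half-width of the 90% CI for one period's mean:

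t(0.95, 13) × s / √14 = 1.7709 × 25 / 3.7417 = 11.8 points.

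*r* does not appear, so the two planned intervals look the same whatever the correlation.

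**Step 2: the within-participant difference.** Half-width = t(0.95, 13) × s × √(2(1 − r)/14). At r = 0 this is 1.7709 × 25 × 0.3780 = 16.73; other values multiply this by √(1 − r).

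**Step 3: periods treated as independent groups.** Half-width = t(0.95, 26) × s × √(2/14) = 1.7056 × 25 × 0.3780 = 16.12.

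| Correlation r | Half-width of paired difference (s = 25) | Ratio to 16.12 |
|---|---|---|
| 0 | 16.7 | 1.04 |
| 0.3 | 14.0 | 0.87 |
| 0.5 | 11.8 | 0.73 |
| 0.7 | 9.2 | 0.57 |

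The match with 11.8 at r = 0.5 arises only because 2(1 − 0.5) = 1.

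**Step 4: reading the table.** The same two planned intervals are compatible with difference intervals that vary by a factor of 16.73 / 9.17 = 1.82. Pairing does not always narrow the interval: the break-even correlation is 1 − (1.7056/1.7709)² = 0.07, and at r = 0 the paired interval is 4% wider. Half-widths scale with *s*: at r = 0.5 they are 7.1 points for an SD of 15 and 14.2 for an SD of 30.

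**Step 5: what can be recovered.** The SD in each period can be worked back from its CI. The variance of the difference also needs *r*, or equivalently the SD of the individual differences, and neither is planned for reporting. This holds for any SD.

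**The case against.** The strongest reply is that the descriptive approach is deliberate and consistent. Protocol 9.1 and 9.3.1 and SAP 5.1 rule out hypotheses and formal tests, and side-by-side summaries are one way to compare. The planned summaries by time point also serve the other taste aims (onset, intensity, duration). All scores are listed, so with 14 participants anyone could compute the paired differences.

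Further points on that side:

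- The candy is always second, 24 hours after the first dose, and open-label. A paired interval would mix candy with period, repeat-dose and expectation effects.
- Seven attributes at four times give 28 intervals. If there were no true difference anywhere, about 28 × 0.10 = 2.8 of the 90% CIs would be expected to exclude zero.
- The Tasso–venous model concerns primary-endpoint parameters from simultaneous samples after one dose, so it has no period confounding. The race ANOVA is between participants.
- Participants stay in the unit from Day -1 to Day 3, so few missing period 2 questionnaires are likely.

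Much of this stands as a limit on weight. The plan does not contradict itself, and the confounding is real. But a difference with a CI is an estimate, not a test, and the PK models show that the no-hypothesis statement was not read as barring such estimates. Computing the difference from listings would be post hoc, with incomplete pairs handled by no stated rule. The confounding affects the separate means equally. The 28 intervals call for exploratory labelling, not for omitting the contrast.

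**Conclusion.** The concern holds. I found no passage in either document that plans a within-participant candy difference or an interval for it. The missing precision does not depend on the assumed SD; only the illustrated sizes do. Those assume complete pairs, equal SDs in the two periods and t-based intervals. The near-twofold spread belongs to the chosen correlation range of 0 to 0.7.

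The risk of unmatched participants is a gap in wording and arises only if period 2 data are missing. This is a worthwhile, low-cost improvement to an exploratory, descriptive analysis, not an error that threatens the primary PK results.

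**What to change.** - In SAP 6.2.2 and Appendix 1, add for each attribute and time point the within-participant difference (period 2 minus period 1), with mean and 90% CI, in participants who have both questionnaires, and report that n. A mixed model with intervention as fixed effect and participant as random effect, in line with SAP 6.1.2, is an alternative.
- In the Taste Assessment Set, state whether the questionnaire is required in one period or both.
- Label all 28 differences exploratory and unadjusted for multiplicity, and state that they are confounded with period because of the fixed order and open-label design. Naming one main attribute and time point in advance would help interpretation.

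The cost is a few lines of SAP text and one table. No new assessments or participants are needed.
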